## 2. **Background:** Describe the background information that led to the plan for this project.

Provide references to support the expectation of obtaining useful scientific data.

Microglia and its interactions with amyloid plaques play an important role in the pathogenesis of Alzheimer's disease (AD), but current methodologies, including animal models, CSF proteomics, histopathology of necropsy tissue and epidemiological approaches, have failed to elucidate the exact role of microglia in the progression of disease (1–4). It is possible that microglia have differing roles in different stages of AD: they may be protective against amyloid accumulation but cause disease progression in later disease. The discovery of translocator protein (TSPO), a mitochondrial protein upregulated with microglial activation, and positron emission tomography (PET) ligands for imaging TSPO present opportunities for better *in vivo* study of neuro-inflammation (5). Amongst these radio-ligands C-PBR28, a newer agent, appears to be superior to earlier ligands for the purposes of *in vivo* imaging of TSPO (6). Using PBR28, a recent NIMH (7) study showed significantly greater microglial activation in early AD compared to normal controls and those with mild cognitive impairment (MCI). Interestingly, MCI subjects did not differ significantly from normal controls in terms of microglial activation. Given that amyloid status in MCI more closely resembles AD than cognitively normal individuals (8), this finding cannot be accounted for by increases in amyloid

load alone. More recently, a longitudinal study using C-(R)-PK11195 PET showed increases in neuro-inflammation in spite of stable amyloid levels over the period of the study (9). The ideal next step would be to assess whether in AD, microglia are more reactive to pathogen and danger associated molecular patterns (PAMPs and DAMPs), which include constituents of both lipopolysaccharide (LPS) and amyloid plaques.

Neuro-inflammation is a hallmark of Alzheimer's disease pathology as evidenced by CSF studies of inflammatory cytokines, necropsy tissue histopathology and most convincingly by genetic studies (12). Microglia, as long lived cells which replenish themselves by division, are vulnerable to the effects of aging and senescence. Even with normal aging the phenotype of microglia appears to become more pro-inflammatory (i.e. reactive microglia). It also seems that compared to young healthy individuals their reaction to immunogens is amplified and prolonged, either as a compensatory mechanism for inefficiencies of aged microglia or due to a loss of regulatory control over these cells (11). For this reason, inflammation was once thought to be an epiphenomenon and a result of over-sensitivity of aging microglia to amyloid plaque constituents. But there is now strong evidence linking neuro-inflammation with pathophysiology of sporadic Alzheimer's disease. In humans, genome wide association studies in patient with sporadic AD show mutations in several genes involved with the innate immune system of the brain (13–27) namely TREM2, CD33, CR1, ABCA7, SHIP1 and APOE.

Neuro-inflammation seen in AD consists of chronic microgliosis and to a lesser extent reactive astrogliosis (28,29). Microglia can be activated either by cytokines (IFN- $\gamma$ ) or when it comes into contact with danger and pathogen associated molecular patterns (PAMPs and DAMPs) (30) such as lipid constituents of the amyloid plaque (31) or lipopolysaccharides (32). In AD the interaction between microglia and the amyloid deposits in the brain is thought to initiate neuro-inflammation in the brain. This inflammatory response was initially thought to be damaging but contrary evidence also exists. Anti-inflammatory strategies in several clinical trials, based on the assumption that neuro-inflammation accelerated AD pathology, not only failed to slow the progression of disease, but in some cases may have accelerated it (33–45). In fact, there is evidence that neuro-inflammation may be protective in certain circumstances. TREM2 gene codes for a receptor that senses the presence of certain lipids within the amyloid plaques and leads to activation of the microglia. It appears that pathogenic mutations in the TREM2 gene (for example R47H) cause a loss of function in TREM2 receptor and that this loss of function leads to diminished protection by neuro-inflammation (1). The problem is that currently little is known about the timing of neuro-inflammation in the course of AD, its relationship to peripheral inflammation, and its exact role in AD pathogenesis. Physiologically microglia appears to have contradictory roles in the progression of Alzheimer's disease: on the one hand it appears to phagocytose amyloid (46) and form a barrier around the plaque which protects adjacent neurites from synaptic loss (47); on the other it may accelerate disease progression especially in the later stages of the disease (12).

The study of neuro-inflammation in Alzheimer's disease has been challenging, partly because the underlying mechanisms are still incompletely understood but also because there is contradictory clinical evidence and a seeming unreliability of mouse models where well designed experiments appear to demonstrate contradictory results. In one study TREM2 knockout reduced pro-inflammatory polarization of microglia and accelerated AD pathology in the 5XFAD mouse models (1). Another group using the APPPS1 mouse model found the elimination of TREM2 positive 'macrophages' and resolution of AD pathology (2). Additionally, the deletion of genes responsible for inflammation in mouse models of AD lead to accelerated progression of the disease suggesting a possible protective role for neuro-inflammation (48–54). Similarly, blocking immunosuppressive cytokines such as TGF- $\beta$ 1, IL-4 and IL-10 improve AD pathology in mouse models (55–61). Conversely, in a study carried out in very young wild type mice using the viral mimic polyribonucleic-polyribocytidilic acid to drive inflammation, there was development of A-beta plaques, tau aggregation, microglia activation and reactive gliosis (62). Additionally, several studies demonstrate a link between the presence systemic inflammation or increased activation of innate immunity, and accelerated AD progression (63–71). There is also evidence for a detrimental role for local inflammation in that A-beta may bind to CD36, TLR4, and TLR6 resulting in inflammation which may lead to intracellular accumulation of amyloid and activation of inflammasomes (50,72,73).

In vivo physiological studies in humans have also been difficult to perform. Although the brain and peripheral immune systems influence each other, the relationship is not a direct one and the central nervous system represents a partially privileged site immunologically. This necessitates the measurement of biomarkers of inflammation in the CSF. However even this method has yielded contradictory results suggesting a heterogeneous phenotypic picture or

technical difficulty (3). Histopathological studies are similarly inconclusive because activation of microglia is not always discernable from morphology of the microglia (4).

The transporter protein imaging therefore represents a major potential advancement in the study of neuro-inflammation in AD. TSPO, previously known as the peripheral benzodiazepine receptor (PBR), is an 18 kDa protein located in the outer mitochondrial membrane which is claimed (sometimes controversially) to subserve a number of physiological functions including steroidogenesis and regulation of the immune response. For the study of inflammation, the most significant property of the molecule is its up regulation during neuro-inflammation in microglia and astroglia (in reactive astrogliosis) (29). Various PET ligands have been developed but until recently these ligands appear to have suffered from a number of problems.

The first and most commonly used TSPO radio-ligand has been PK11195, however it suffers from a number of important shortcomings: 1- It has poor pharmacokinetics and washes out too quickly (74). 2- It has relatively weak binding to TSPO and is lipophilic so that signal to noise ratio is relatively poor (75). 3- There are technical difficulties with calculating binding because metabolite-corrected arterial plasma input curve is impractical due to ligand binding to plastic tubing and the simplified reference tissue model is complicated by a lack of such a reference region in neurodegenerative diseases (76,77). There are 15 reported human studies of PK11195 in AD. These studies have yielded inconsistent results: One study (78) showed increased inflammation in the cortex of AD patients, four studies did not report a statistical difference between the case and control groups (79–82). Another four studies reported the absence of statistical differences between the two groups (83–86). A further two showed equivocal results with one showing a difference between controls and MCI and not AD (87) and the other showing no difference with region of interest analysis but small areas of inflammation in the occipital lobe on voxel-wise statistical parametric mapping (88). The remaining four smaller studies show widespread inflammation in the cortex and subcortex including temporal (89–92), parietal (89,91,92), frontal (89–92), occipital (89,91) and cingulate (89,91) cortices as well as cerebellum (89,91), amygdala (89,91), putamen (89) and pallidum (89).

Several second generation TSPO radio-ligands have been developed including DAA1106, vincopectine and PBR28. These agents have much higher affinity for TSPO and better pharmacokinetics. However, some of these ligands have yet to live up to their original promise. Two studies (93,94) with 11C-DAA1106 showed widespread uptake including in some parts of the brain such as the striatum and cerebellum which are not commonly thought to be affected by disease. Part of the problem may have been the relative slow washout of DAA1106 compared to the short half-life of C11, confounding accurate measurement of binding. 18F-FEEDAA1106, a higher binding related compound, was used in another study and no increase in inflammation was reported. Similarly, a study using 11C-vincopectine showed no effect (95).

For this study we choose PBR28. Amongst TSPO ligands PBR28 seems to have the most desirable characteristics for inflammatory imaging in AD: It has very high affinity for TSPO and an excellent signal-to-noise ratio (96). The main problem with this ligand, shared by all TSPO ligands except PK11195, is the variable specific binding of PBR28 due to TSPO gene polymorphism (rs6971) (97,98). The method used for adjusting for this fact involves genotyping TSPO (or using a competitive binding assay) and excluding low affinity binders. For the mixed (heterozygous for the polymorphism) and high affinity binders compensatory changes can be made in calculating binding (6,99–101). Four studies thus far have used PBR28 in Alzheimer's disease but only one attempted to directly compare AD patients with MCI and cognitively normal patients. This particular study was conducted at the molecular imaging branch of National Institute of Mental Health7, which compared 19 AD, 10 MCI and 13 amyloid negative controls for TSPO binding. Patients with AD showed increased binding especially in the temporal and parietal lobes. Additionally, there were correlations between TSPO binding and neuropsychological as well as volumetric parameters. Another group (102) performed a genome wide association study of longitudinal accumulation of amyloid independent of APOE status. They found carriers of IL1RAP rs12053868 had faster progression and worse atrophy compared to non-carriers. In a different cohort the same gene polymorphism was associated with lower cortical binding of 11C-PBR28 suggesting a protective role for inflammation. In yet another study (103), the same group showed a relationship between PBR28 binding and PPAR1 polymorphism, and they inversely correlated PBR28 and cortical atrophy.

Innate immunity, mediated by microglia, plays an important role in the pathogenesis of Alzheimer's disease. As discussed above, several genes implicated in microglial function are risk factors for late onset AD. TREM2 one of the genes with the highest odds ratios for AD risk, codes for a membrane protein which is involved in the interaction of

the microglia with constituents of the amyloid plaques. The NIMH study (7) of PBR28 binding in patients with AD, MCI and normal cognition showed increased binding in the AD group compared to the other two groups. Equally as important was the finding that there was no significant difference in the PBR28 binding of MCI patients compared to normal controls. Most of amyloid deposition occurs before the onset of symptoms and the rate of amyloid increase plateaus in MCI, so that patients in early AD on average have a relatively small increment in their amyloid deposition compared to MCI (8). The difference in immune activation in AD and MCI may represent differing microglial sensitivity to molecular patterns that activate them for example amyloid plaques. To test this hypothesis, we need to know both the state of activation of microglia and the microglia capacity to activate (activation reserve) which we have defined as reactivity of microglia to a given stimulus. Activation status of microglia depends on a variety of factors including the presence of peripheral inflammation, age and the amount of amyloid present in the brain, whereas microglial activation reserve is more likely influenced by genetics, senescence and regulation of microglia.

LPS activates the same immune mechanisms which are involved in the immunological responses to amyloid deposition (104,105). We earlier showed the activation of microglia in the nervous system in response to peripheral administration of LPS in non-human primates (106). We then went on to apply this to healthy human volunteers who showed a robust response to LPS administration (10). The imaging protocol involves a baseline PBR28 scan which will be compared to a post-LPS scan. Percentage change is likely to be the most meaningful measure ( $MARI=[(VT(LPS)-VT(baseline))/ VT(baseline)] \times \%100$ ). Our previous study in baboon showed the predominant binding of TSPO immunoreactivity is to microglia and not to astroglia, the other kind of cell also capable of expressing TSPO. Furthermore, the use of 0.1 mg/kg and 1 ng/kg of LPS in baboon and humans respectively showed similar magnitude of change in the activation of microglia. This is important as much higher doses of LPS is likely to have detrimental effects on the health of subjects and may be symptomatically more burdensome. For this experiment our calculations will be made for the parietal region of interest as this was the area most activated by LPS administration in our healthy controls and showed the greatest amount of baseline activation amongst AD subjects in the NIMH study.

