minutes post LPS. We define microglia activation reserve index (MARI) as the proportional increase in binding of PBR28, 180 minutes after the administration of the LPS:  $MARI = [(VT(LPS)-VT(baseline))/ VT(baseline)] \times 100$ . In a previous study, we demonstrated the feasibility and robustness of this technique by applying this methodology to 8 healthy volunteers showing 30-60% increase in PBR28 binding after LPS administration (10). We predict increased MARI in patients with early AD compared to cognitively normal aged matched individuals. Given that we also have data from young healthy individuals from our earlier study, we can explore whether the microglia activation reserve index is increased in microglia with aging (which we predict to be the case). We can gauge also whether the changes in MARI in AD represent incremental increases compared to normal aging or that a significant dysregulation of innate immunity occurs in AD. With this experiment we aim to:

Aim - Examine the differences in the capacity to activate microglia in patients with AD compared to age-comparable cognitively normal subjects and younger healthy controls.

Hypothesis: In early AD the innate immune response becomes more reactive to PAMPs and DAMPs compared to those with normal cognition.

Our primary outcome is MARI (calculated in the parietal ROIs) in AD patients compared to elderly controls. We will use 7 AD and 7 comparably aged cognitively normal successfully scanned subjects to calculate the microglial activation reserve index. We expect significant differences between the two groups suggesting increased reactivity of the microglia in AD. The reverse would suggest a burn-out phenomenon which we expect to occur in a later stage of the disease but not in our study cohort. This result would be an exciting one suggesting at least one mechanism by which some patients with significant amyloid load have progressive dementia while comparable others are either cognitively normal or have stable MCI. It will also suggest avenues for intervention in amyloid positive MCIs to prevent progression to Alzheimer's dementia. Our exploratory analysis will include:

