**PET Imaging of TSPO in AD**

We will compare PBR28 binding site availability in brain regions of 7 living human subjects who have AD with that in 7 age-matched healthy controls by using the ligand  $^{11}\text{C}$ -PBR28 and PET. Dose of LPS (see below) will be administered intravenously and the subject will be reimaged at 180 minutes after the injection. Considering possible failures in scans, a total of 16 patients will be studied in 2 groups, cognitive normal AND amyloid negative versus clinical criteria for mild AD and amyloid positive to reach our goal of 7 successfully scanned subject for each group. The detailed protocol may be found

09/29/12 Version 13

in our previous publication (109). We expect that 20-30% of cognitively normal participants who receive amyloid scans under this protocol will be amyloid positive. Therefore, we will enroll up to 10 participants in the cognitively normal cohort to attain the goal of 7 participants who are cognitively normal AND amyloid negative.

Primary Outcome:

The 16 enrolled subjects will have C-PBR28 using the bolus/infusion method. Measurements will be made at baseline and 180 minutes after the injection of LPS. We will measure Total Volume of Distribution (VT) for 12 brain regions defined by MRI scan, as described (111). All primary outcomes will use the parietal ROI for calculations of both baseline activation and microglial activation reserve. For our primary outcomes we will choose the microglia activation reserve index defined as MARI =  $[(VT(LPS)-VT(\text{baseline}))/ VT(\text{baseline})] \times 100$ . In the NIMH study the greatest difference in the regional PBR28 binding between AD and cognitively normal subjects was found in the parietal lobe (7). We also found the greatest microglia activation reserve index in the parietal lobe when we applied our paradigm to young healthy controls (109). Other ROIs will be used in secondary analyses.

Statistical Considerations and Sample Size:

Several comparisons of C-PBR28 VT brain level and microglia activation reserve index in the parietal lobe will be made using Student T-test to test for a difference between group means: young healthy group vs. elderly cognitively normal, as well as AD vs. elderly cognitively normal.

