**Expected Result**

1- Baseline binding: We expect increases in baseline binding (i.e. volume of distribution) of PBR28 in the parietal

lobe. This is both where most of the amyloid is deposited in early disease and also the location of the strongest positive findings in the NIMH study.

2- Microglia activation reserve index: We also expect to have significant up-regulation of the microglia activation reserve index. The calculations will be done using the parietal lobe ROI, this is the region that shows the most inflammatory response in our previous study of normal patient with LPS and also where most marked change in the PBR28 binding was found in the NIMH study. However we expect increases in the inflammatory response in the brain diffusely especially affecting the parts which were shown to have increased inflammation at baseline such as precuneus and mesial temporal areas.

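### MARI divides by a baseline VT that the plan expects to be higher in AD. Add absolute VT change as a sensitivity analysis and limit the burn-out reading.

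*Combined protocol and SAP*

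**What the plan says.** Section V.1 (Statement of Purpose) sets the index: "We define microglia activation reserve index (MARI) as the proportional increase in binding of PBR28" after LPS, that is, 100 × (VT after LPS − VT baseline) / VT baseline. The same section sets the contrast: "Our primary outcome is MARI (calculated in the parietal ROIs) in AD patients compared to elderly controls". On numbers it says "We will use 7 AD and 7 comparably aged cognitively normal successfully scanned subjects".

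The Background supports the percentage scale only with the remark that "Percentage change is likely to be the most meaningful measure". It chooses the parietal region partly because that region "showed the greatest amount of baseline activation amongst AD subjects in the NIMH study". Under Expected Result the plan repeats the expectation for this trial: "We expect increases in baseline binding (i.e. volume of distribution) of PBR28 in the parietal" lobe.

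Section V.1 reads a higher MARI in AD as increased reactivity. For a lower MARI it says "The reverse would suggest a burn-out phenomenon", which the plan expects in later disease and not in this cohort.

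The statistical text, given under PET Imaging of TSPO in AD and again under Statistical Considerations, plans t-tests on parietal VT and on MARI. It names no analysis of the absolute change in VT. The Pitfalls and Limitations list does not mention the denominator.

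**The concern.** The Background treats the current activation of microglia and their capacity to activate as separate quantities with different determinants. Yet the index for the second has the first as its denominator, and the plan expects the groups to differ on that denominator in the region chosen for the primary analysis.

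If LPS adds about the same amount of binding whatever the starting level, a higher baseline lowers MARI by arithmetic. Two errors could follow. A true increase in reactivity in AD could be masked, which works against the trial's own hypothesis. Or a lower MARI could be taken as evidence of burn-out when it shows only a higher baseline. The pilot is meant to inform a larger project, so an unexamined artefact of scale would carry forward.

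**Working it through.** **Inputs from the documents.** 7 evaluable subjects per group; Student t-test; alpha 0.05 (sidedness not stated, two-sided taken here); power 0.80; a 30-60% rise in young volunteers given 1.0 ng/kg.

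**Assumptions.** Control MARI of 45%, the middle of that range; the planned dose here is 0.4 ng/kg, so the true value may differ. AD baseline excess f of 10%, 20% or 40%. Between-subject SD of MARI of 10, 15 or 20 points. The documents give neither f nor this SD.

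**The plan's own figure.** For baseline VT the plan states a detectable effect above 1.6. A two-sided t-test with 7 per group (noncentral t) detects 1.63 SD with 80% power, and power at 1.6 is 0.785, so the figure reproduces. The figure of more than 2 for MARI does not follow from the same inputs if it is in SD units (power at 2 is 0.93). Nothing below rests on it.

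**Dilution if the response is additive.** With equal absolute rises, MARI in AD = MARI in controls / (1 + f).

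- f = 10%: 45/1.1 = 40.9, a shift of −4.1 points
- f = 20%: 45/1.2 = 37.5, a shift of −7.5 points
- f = 40%: 45/1.4 = 32.1, a shift of −12.9 points

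Starting from 30% or 60% instead of 45% gives 27.3 or 54.5 at f = 10%, 25.0 or 50.0 at 20%, and 21.4 or 42.9 at 40%.

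**Chance that the t-test rejects for this reason alone** (d = shift/SD, 7 v 7, two-sided 0.05):

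| f | SD 10 | SD 15 | SD 20 |
|---|---|---|---|
| 10% | 0.11 | 0.08 | 0.06 |
| 20% | 0.25 | 0.14 | 0.10 |
| 40% | 0.60 | 0.31 | 0.20 |

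Almost all of these rejections are in the direction of a lower MARI in AD. As a cross-check, I used a simulation with lognormal baselines, based on the grey-matter VT values in the preliminary results (3.7 ± 1.0 and 3.9 ± 1.4). At f = 20% the AD mean MARI is below controls in 84-87% of trials and significantly below in 12-15%. The same data tested as absolute change reject in about 5%.

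**Masking.** For MARI merely to be equal, the absolute rise in AD must be (1 + f) times that in controls. If the true rise is 30% larger and the baseline 30% higher, MARI is 45% in both groups. If the baseline is 40% higher, MARI in AD is 45 × 1.3/1.4 = 41.8%, so a real increase points the wrong way.

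**How large f might be.** The plan says 1.6 SD is close to the earlier NIMH finding. On the VT values above, f would be 1.6 × 1.0/3.7 = 43% to 1.6 × 1.4/3.9 = 57%, and MARI in AD 31.4% to 28.6%. Those values come from MS patients and younger controls, so this only illustrates. In the other direction, the amyloid PET and Targeted Enrollment sections call the patient cohort MCI, a group that the Background says did not differ from controls at baseline. The excess could therefore be small.

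**The opposite case.** Suppose true MARI is 45% in both groups and only baseline differs. In a simulation with baseline CV 27-36% (from the same VT values) and MARI SD 10-20, absolute change is significantly higher in AD in about 7-14% of trials at f = 20% and 15-36% at f = 40%.

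**The case against.** The strongest reply is that the plan defines reserve as a proportional increase. If binding rises in proportion to baseline, MARI is the right measure and absolute change is inflated in AD, in favour of the trial's hypothesis. This stands: the documents hold no data to choose between the scales, so absolute change cannot replace MARI.

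The second reply concerns genotype. The Background calls rs6971-dependent binding the main problem with the ligand, and exclusion criterion 20 removes only low-affinity binders, so high- and mixed-affinity subjects are pooled. A percentage change largely cancels a genotype scale factor and a raw VT difference does not. This stands too, and it is why the fix carries genotype as a factor.

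Third, parietal VT is itself compared between groups, so a reader would see a baseline difference beside MARI. That helps, but the plan does not say how such a difference should bear on the reading of MARI.

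A reader might infer that the plan will declare burn-out whenever MARI is lower. The text does not go so far: it says only that this result would suggest it, in a purpose statement for a pilot, and does not expect it here. The Interpretation section addresses only a higher MARI. For that result an additive artefact is conservative, because a higher MARI on a higher baseline generally implies a higher absolute change as well.

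**Conclusion.** The point holds as a conditional one and supports a cheap improvement. If the response is additive and baseline is higher in AD, MARI is lowered by the factor 1/(1 + f). With 7 per group, significance for that reason alone arises in about 6-11%, 10-25% or 20-60% of trials at f = 10%, 20% or 40%. At an excess of 10-20% the likelier harm is a masked increase or a misleading direction, not a significant false reversal.

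The stronger statement, that an identical microglial response must give a lower MARI in AD, is not supported. It needs identical to mean an equal absolute rise, and under a proportional response MARI is unbiased. The sizes rest on the assumed 45%, f and SD.

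**What to change.** Keep MARI as the primary outcome.

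1. In the statistical text under PET Imaging of TSPO in AD and under Statistical Considerations, pre-specify a sensitivity analysis: parietal absolute change (VT after LPS minus VT baseline), AD v elderly controls, with rs6971 genotype (high v mixed affinity) as a factor. Report the estimate and confidence interval beside MARI and beside baseline VT by group.
2. In Section V.1, state that a lower MARI in AD will be described as burn-out only if the absolute-change estimate and its confidence interval also support a smaller response. Otherwise, report that the MARI difference cannot be separated from the difference in baseline binding.

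Do not make the conclusion depend on whether the two estimates have the same sign. In simulated trials with no true group difference, the signs disagree by noise alone in about 18-33%. Nor should a disagreement be attributed to baseline binding as if that were established.

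The cost is a few sentences and one analysis of the same two scans. There are three downsides. Absolute change is more sensitive to genotype. It has the opposite bias under a proportional response, so true burn-out becomes harder to claim: at f = 20% or 40%, MARI must fall from 45% to below 37.5% or 32.1% before the expected absolute change is lower at all. And the two scales may disagree, which makes the conclusion more cautious.
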